### **2.3. Benefit/Risk Assessment of Pemigatinib**

Targeted therapies with a manageable safety profile that can provide a durable response or significant disease control in a molecularly defined population would provide a meaningful clinical benefit.

Pemigatinib has been administered to well over 800 patients across 5 different studies and many different tumor types.

The comprehensive safety data that are included in [IB](#) Edition 7 used a data cutoff date of 25 NOV 2020. As of the data cutoff date, a total of 894 participants (133 healthy participants and 761 participants with advanced malignancies) were enrolled in the ongoing clinical studies and received at least 1 dose of pemigatinib. A total of 665 participants received pemigatinib monotherapy for advanced malignancies in 5 ongoing, open-label, nonrandomized studies (Studies INCB 54828-101, -102, -201, -202, and -207) as of the data cutoff date (25 NOV 2020). Of these, 404 participants received intermittent dosing and 261 participants received continuous dosing of pemigatinib. Overall, 663 participants (99.7%), including 403 participants (99.8%) who received intermittent dosing and 260 participants (99.6%) who received continuous dosing, had at least 1 TEAE. In the total population, the most frequently reported TEAEs were HP (394 participants [59.2%]) and diarrhea (277 participants [41.7%]; see [Table 7](#)). Additional details are presented in the following section.

**Table 7: Summary of Treatment-Emergent Adverse Events Occurring in  $\geq 10\%$  of Total Participants Receiving Pemigatinib Monotherapy for Advanced Malignancies**

MedDRA Preferred Term, n (%)	ID (N = 404)	CD (N = 261)	Total a (N = 665)
Hyperphosphataemia	212 (52.5)	182 (69.7)	394 (59.2)
Diarrhoea	174 (43.1)	103 (39.5)	277 (41.7)
Alopecia	174 (43.1)	100 (38.3)	274 (41.2)
Stomatitis	146 (36.1)	125 (47.9)	271 (40.8)
Dysgeusia	134 (33.2)	94 (36.0)	228 (34.3)
Fatigue	152 (37.6)	75 (28.7)	227 (34.1)
Dry mouth	128 (31.7)	97 (37.2)	225 (33.8)
Constipation	137 (33.9)	85 (32.6)	222 (33.4)
Decreased appetite	127 (31.4)	71 (27.2)	198 (29.8)
Nausea	131 (32.4)	67 (25.7)	198 (29.8)
Dry eye	84 (20.8)	56 (21.5)	140 (21.1)
Vomiting	90 (22.3)	44 (16.9)	134 (20.2)
Anaemia	71 (17.6)	54 (20.7)	125 (18.8)
Dry skin	70 (17.3)	49 (18.8)	119 (17.9)
Arthralgia	71 (17.6)	43 (16.5)	114 (17.1)
Asthenia	60 (14.9)	54 (20.7)	114 (17.1)
Abdominal pain	79 (19.6)	31 (11.9)	110 (16.5)
Urinary tract infection	69 (17.1)	37 (14.2)	106 (15.9)
Back pain	69 (17.1)	35 (13.4)	104 (15.6)
Blood creatinine increased	50 (12.4)	52 (19.9)	102 (15.3)
Palmar-plantar erythrodysaesthesia syndrome	40 (9.9)	55 (21.1)	95 (14.3)
Weight decreased	60 (14.9)	32 (12.3)	92 (13.8)
Pain in extremity	54 (13.4)	36 (13.8)	90 (13.5)
Hypophosphataemia	65 (16.1)	19 (7.3)	84 (12.6)
Epistaxis	46 (11.4)	32 (12.3)	78 (11.7)
Hypercalcaemia	47 (11.6)	29 (11.1)	76 (11.4)
Oedema peripheral	43 (10.6)	31 (11.9)	74 (11.1)
Hyponatraemia	40 (9.9)	32 (12.3)	72 (10.8)
Pyrexia	50 (12.4)	21 (8.0)	71 (10.7)
Dehydration	43 (10.6)	24 (9.2)	67 (10.1)
Onycholysis	36 (8.9)	31 (11.9)	67 (10.1)

CD = continuous dosing; ID = intermittent dosing.

Note: Participants were counted only once under each MedDRA preferred term.

Note: MedDRA preferred terms were presented in descending order of frequency using the total column.

a Includes participants from Studies INCB 54828-101, -102, -201, -202, and -207.

**Table 8** presents a summary of serious TEAEs by preferred term that occurred in  $\geq 1\%$  of total participants with advanced malignancies who received pemigatinib monotherapy. In the total population, 297 participants (44.7%) who received monotherapy had a serious TEAE. In participants who received intermittent dosing, 184 participants (45.5%) had a serious TEAE; in

participants who received continuous dosing, 113 participants (43.3%) had a serious TEAE. In the total population, the most frequent serious TEAEs were urinary tract infection (21 participants [3.2%]) and abdominal pain and acute kidney injury (17 participants [2.6%] each). The most frequent serious TEAEs that were considered to be related to pemigatinib by the investigator were hyponatremia (4 participants [0.6%]), fatigue and anemia (3 participants [0.5%] each), and diarrhea, stomatitis, nausea, and hypercalcemia (2 participants [0.3%] each).

**Table 8: Summary of Serious Treatment-Emergent Adverse Events Occurring in  $\geq 1\%$  of Total Participants Receiving Pemigatinib Monotherapy for Advanced Malignancies**

MedDRA Preferred Term, n (%)	ID (N = 404)	CD (N = 261)	Total a (N = 665)
Urinary tract infection	10 (2.5)	11 (4.2)	21 (3.2)
Abdominal pain	12 (3.0)	5 (1.9)	17 (2.6)
Acute kidney injury	10 (2.5)	7 (2.7)	17 (2.6)
Pyrexia	13 (3.2)	2 (0.8)	15 (2.3)
General physical health deterioration	7 (1.7)	8 (3.1)	15 (2.3)
Back pain	7 (1.7)	8 (3.1)	15 (2.3)
Pneumonia	10 (2.5)	4 (1.5)	14 (2.1)
Hyponatraemia	8 (2.0)	5 (1.9)	13 (2.0)
Pleural effusion	9 (2.2)	2 (0.8)	11 (1.7)
Disease progression	5 (1.2)	6 (2.3)	11 (1.7)
Cholangitis	8 (2.0)	2 (0.8)	10 (1.5)
Small intestinal obstruction	9 (2.2)	1 (0.4)	10 (1.5)
Anaemia	5 (1.2)	4 (1.5)	9 (1.4)
Constipation	6 (1.5)	3 (1.1)	9 (1.4)
Sepsis	6 (1.5)	3 (1.1)	9 (1.4)
Fatigue	4 (1.0)	4 (1.5)	8 (1.2)
Haematuria	8 (2.0)	0	8 (1.2)
Blood creatinine increased	4 (1.0)	3 (1.1)	7 (1.1)
Decreased appetite	4 (1.0)	3 (1.1)	7 (1.1)
Dehydration	4 (1.0)	3 (1.1)	7 (1.1)
Dyspnoea	4 (1.0)	3 (1.1)	7 (1.1)
Hypercalcaemia	5 (1.2)	2 (0.8)	7 (1.1)
Vomiting	5 (1.2)	2 (0.8)	7 (1.1)

CD = continuous dosing; ID = intermittent dosing.

Note: Participants were counted only once under each MedDRA preferred term.

Note: MedDRA preferred terms were presented in descending order of frequency using the total column.

a Includes participants from Studies INCB 54828-101, -102, -201, -202, and -207.

In the total population, serious TEAEs with a fatal outcome occurred in 64 participants (9.6%). In participants who received intermittent dosing, TEAEs with a fatal outcome occurred in 37 participants (9.2%); in participants who received continuous dosing, TEAEs with a fatal outcome occurred in 27 participants (10.3%). In the total population, fatal TEAEs that occurred in  $> 2$  participants were general physical health deterioration (15 participants [2.3%]), disease progression (10 participants [1.5%]), malignant neoplasm progression and sepsis (4 participants [0.6%] each), and dyspnea and failure to thrive (3 participants [0.5%] each).

In the total population, 71 participants (10.7%) discontinued pemigatinib treatment because of a TEAE. In participants who received intermittent dosing, 39 participants (9.7%) discontinued

pemigatinib treatment because of a TEAE; in participants who received continuous dosing, 32 participants (12.3%) discontinued pemigatinib treatment because of a TEAE. In the total population, the most frequent TEAEs that led to discontinuation of pemigatinib were disease progression (5 participants [0.8%]), general physical health deterioration (4 participants [0.6%]), and sepsis, acute kidney injury, and intestinal obstruction (3 participants [0.5%] each). In participants who received intermittent dosing, the most frequent TEAEs that led to discontinuation of pemigatinib were acute kidney injury (3 participants [0.7%]) and pneumonia, general physical health deterioration, small intestinal obstruction, malignant neoplasm progression, disease progression, and intestinal obstruction (2 participants [0.5%] each). In participants who received continuous dosing, the most frequent TEAEs that led to discontinuation of pemigatinib were disease progression (3 participants [1.1%]) and stomatitis, general physical health deterioration, and sepsis (2 participants [0.8%] each).

There were no dose-limiting toxicities in participants receiving monotherapy.

More detailed information about the known and expected benefits and risks (clinical safety and nonclinical toxicology) and reasonably expected AEs of pemigatinib are provided in the [IB](#).

### 3. OBJECTIVES AND ENDPOINTS

Table 9 presents the objectives and endpoints.

**Table 9: Objectives and Endpoints**

Objectives	Endpoints
Primary	
To evaluate the efficacy of pemigatinib in participants with locally advanced/metastatic or surgically unresectable solid tumor malignancy with an activating FGFR mutation or fusion/rearrangement.	ORR in Cohort A, defined as the proportion of participants in Cohort A who achieve a CR or PR based on RECIST v1.1 or RANO. ORR in Cohort B, defined as the proportion of participants in Cohort B who achieve a CR or PR based on RECIST v1.1 or RANO. An independent radiological review committee will determine response.
Secondary	

To evaluate other clinical efficacy measurements of pemigatinib in participants with locally advanced/metastatic or surgically unresectable solid tumor malignancy with an activating FGFR mutation and/or fusion/rearrangement.

Safety and tolerability of pemigatinib.

	

PFS, defined as the time from first dose until progressive disease (according to RECIST v1.1 or RANO and assessed by an ICR) or death (whichever is first) in Cohorts A and B, respectively.

DOR, defined as the time from the date of first assessment of CR or PR until the date of the first progressive disease by an ICR per RECIST v1.1 or RANO, or death (whichever is first) in Cohorts A and B, respectively.

OS, defined as the time from first dose of study drug to death of any cause in Cohorts A and B, respectively.

Safety and tolerability, as assessed by the occurrence of TEAEs and treatment-related AEs according to NCI CTCAE v5.0, physical exam changes, vital sign changes, laboratory evaluations, and ECGs in each cohort.

**Table 9: Objectives and Endpoints (Continued)**

Objectives	Endpoints
REDACTED	

## 4. STUDY DESIGN

### 4.1. Overall Design

This is an open-label, monotherapy study of pemigatinib in participants with advanced/metastatic or surgically unresectable solid tumor malignancy harboring an activating FGFR mutation or fusion/rearrangement. This study consists of 3 cohorts, Cohort A, Cohort B, and Cohort C and will enroll approximately 60 participants, 90 participants, and 20 participants, respectively.

Participants will receive a QD dose of pemigatinib at 13.5 mg continuously as long as participants are receiving benefit and have not met any criteria for study withdrawal.

Participants with local laboratory test results (eg, tissue or plasma-based molecular assays) documenting an activating FGFR1, FGFR2, or FGFR3 mutation or gene rearrangement are eligible to enroll as long as the results meet the cohort criteria. Confirmatory testing through the central genomics laboratory will be performed for all participants; however, results from the central genomics laboratory are not required before enrollment. Patients who have a commercial report at screening from the central laboratory (Foundation Medicine, Inc) within 24 months of screening will not need to send a sample for confirmatory testing (a biopsy will still be required for other testing). Centralized genomic testing results will allow participants to be assigned to a cohort (see [Appendix C](#) for list of alterations):

- Cohort A: FGFR1-3 in-frame fusions; any FGFR2 rearrangement; FGFR1/3 rearrangement with known partner\* (n = 60)
- Cohort B: Known or likely activating mutations (excluding kinase domain) in FGFR1-3 included in [Appendix C](#) (n = 90)

- Cohort C: FGFR1-3 known activating mutations in kinase domain; FGFR1-3 putatively activating mutations; other FGFR1/3 rearrangements\* (not eligible for Cohort A; n = 20)

\*Only FGFR fusions or rearrangements with an intact kinase domain are eligible.

Please note that there is no difference in the treatment regimen between the cohorts. The sponsor may choose to cap enrollment of any one tumor type and/or FGFR alteration to allow representation of multiple tumor types and avoid analysis being influenced by any one tumor type. The sponsor may also choose to cap enrollment of any one tumor type if no benefit is being seen in previous participants enrolled.

For participants with FGFR2-rearranged cholangiocarcinoma, enrollment is limited to no more than 10 participants into Cohort A; for participants with FGFR3 mutation or fusions bladder cancer, enrollment is limited to no more than 10 participants into Cohort A or B combined. Participants from either group noted must have mandatory baseline and at least 1 on-treatment biopsy.

A fresh biopsy at baseline (or archival tissue that was collected less than 24 months from date of screening) and at least 1 on-treatment biopsy is required for participants for patients in the biopsy subset with safely accessible lesions. Treatment will start on Day 1. Participants will undergo regular safety assessments during treatment as well as regular efficacy assessments. Participants will be allowed to continue administration in 21-day cycles until documented disease progression or unacceptable toxicity is reported.

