## **10. STATISTICS**

### **10.1. Sample Size Determination**

For Cohort A, approximately 60 participants are planned. Assuming the true ORR is 35% for the intervention in this group, 60 participants are needed to ensure that there is at least 90% power to test the null hypothesis of  $ORR \leq 15\%$ . This calculation assumes 1-sided test at the overall 0.025 level of significance.

For Cohort B, approximately 90 participants are planned. Assuming the true ORR is 30% for the intervention in this group, 90 participants are needed to endure that there is at least 90% power to test the null hypothesis of  $ORR \leq 15\%$ . This calculation assumes 1-sided test at the overall 0.025 level of significance.

For Cohort C, approximately 20 participants will be enrolled, which will provide at least 80% chance of observing at least 4 responders in this cohort if the underlying ORR is 30%.

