### **10.3. Level of Significance**

The overall level of significance is 1-sided 0.025. The primary endpoint in Cohort A and Cohort B will be tested sequentially at 1-sided 0.025. If ORR in Cohort A is significant, then ORR in Cohort B will be tested.

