7.1. Efficacy Hypotheses

Objective Response Rate (Primary Endpoint): Administration of pemigatinib to participants in Cohort A and B improves ORR from 15%. Assume ORR_A and ORR_B are the ORRs for cohort A and B respectively.

The hypotheses for Cohort A are as follows:

- H_0 (null hypothesis): $ORR_A \leq 15\%$
- H_A (alternative hypothesis): $ORR_A > 15\%$

The hypotheses for cohort B are as follows:

- H_0 (null hypothesis): $ORR_B \leq 15\%$
- H_A (alternative hypothesis): $ORR_B > 15\%$

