7.2.2. Subgroup Analyses for Primary Endpoint

Subgroup analysis of the primary endpoint will be performed based on appropriate intrinsic and extrinsic factors if needed.

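### If a tumor type is capped for lack of benefit, the pooled ORR describes a mix partly chosen on its own results, and the plan neither reports nor limits the claim accordingly

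*Protocol*

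**What the plan says.** Protocol 4.1 (Overall Design) contains three kinds of enrollment limit, and SAP 3 repeats them.

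- A cap for balance: "The sponsor may choose to cap enrollment of any one tumor type and/or FGFR alteration to allow representation of multiple tumor types".
- Fixed numerical caps: "For participants with FGFR2-rearranged cholangiocarcinoma, enrollment is limited to no more than 10 participants into Cohort A". FGFR3 bladder cancer has a similar limit of 10 across Cohorts A and B.
- A cap driven by results: "The sponsor may also choose to cap enrollment of any one tumor type if no benefit is being seen in previous participants enrolled".

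For the third, neither document gives a threshold, a minimum number treated, a response source (local or central), a decision-maker or a record. Protocol 6.3 states that there is no blinding.

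On inference, Protocol 10.3 says: "The primary endpoint in Cohort A and Cohort B will be tested sequentially at 1-sided 0.025". Cohort B is tested only if Cohort A is significant. Both null hypotheses are an ORR of at most 15% (SAP 7.1). Protocol 10.4.1 and SAP 7.2.1 specify an exact binomial p-value and a Clopper-Pearson interval on all treated participants in the cohort. The sections on sample size, type I error and interim analysis do not mention capping.

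The only named sensitivity analysis of ORR uses the per protocol population (SAP 7.2.3). On subgroups, SAP 7.2.2 says: "Subgroup analysis of the primary endpoint will be performed based on appropriate intrinsic and extrinsic factors if needed". Tumor type is not named there.

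**The concern.** The balance cap and the two caps of 10 do not depend on whether the type responds. The third cap does: it removes a type because of the primary outcome and passes its remaining places to the other types. The final mix then depends on the responses being tested.

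The primary objective (Protocol 3) concerns FGFR-altered solid tumors generally. After response-driven capping, the pooled ORR answers a narrower question about the types that stayed open. A result above 15% could reflect drug effect, selection of the mix, or both. With subgroup analysis optional, the plan does not guarantee that a reader could tell these apart.

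**Working it through.** **Inputs from the documents.** Null ORR 15%, 1-sided 0.025, N = 60 (A) and 90 (B), alternatives 35% and 30% (Protocol 10.1 and 10.3, SAP 7.1).

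**Step 1: reproduce the plan.** Take the smallest r with P(X >= r | N, 0.15) <= 0.025.
- Cohort A: r = 16 of 60. Actual size 0.0136; power P(X >= 16 | 60, 0.35) = 93.4%.
- Cohort B: r = 21 of 90. Actual size 0.0240; power P(X >= 21 | 90, 0.30) = 93.5%.

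Both meet the stated floor of 90%. The sample size is sound for a mix that does not depend on results.

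**Step 2: when the level is kept.** If every type has a true ORR of at most 15%, each new participant responds with probability at most 0.15 whatever has been closed before. The responder count is then stochastically no larger than Binomial(N, 0.15). Simulation with all types at 15% agrees: 1.2-1.6% in A and 2.4-2.8% in B, with or without closure.

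**Step 3: when types differ.** Everything here beyond N and r is assumed: six equally common types, three at 5% and three at 25%, so the uncapped ORR is (5% + 25%)/2 = 15%. A type closes after 0 responders in its first 5 or 8 evaluated participants. Results become known after a lag of 0, 10 or 20 further enrollments. There were 6,000 simulated trials per setting (standard error about 0.002 at a probability of 0.02). Chance of success at the planned cut-off:

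| Cohort | Closure | Lag 0 | Lag 10 | Lag 20 |
|---|---|---|---|---|
| A | 0/5 | 6.3% | 3.5% | 2.3% |
| A | 0/8 | 1.6-2.2% over the three lags | | |
| B | 0/5 | 21.0% | 14.3% | 10.2% |
| B | 0/8 | 8.6% | 6.1% | 4.4% |

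With closure after 0/5, the mean pooled ORR rises from 15% to 18.0, 16.8 and 15.8% in A, and to 19.1, 18.2 and 17.5% in B.

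**Step 4: direct check of the mechanism.** If the 25% types make up 70% of the final cohort instead of half, the enrolled ORR is 0.7 x 25% + 0.3 x 5% = 19%. With those shares fixed, the exact chance of success is 0.086 (A) and 0.173 (B), against 0.010 and 0.019 at a 50:50 split.

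**Step 5: sensitivity to the assumptions.**
- Twelve equally common types at 5%/25%: about 1-2% in A and 2.5-8% in B.
- Six types at 10%/20%: A 1.2-1.9%, B 2.5-4.8%.
- Six types at 0%/30%: after 0/5, A 4.0-24.0% and B 33.9-69.2%; after 0/8, A 1.3-5.9% and B 12.2-41.7%.

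**Step 6: gatekeeping.** The Cohort B figures are marginal. If both cohorts had an uncapped ORR of 15% and were independent, the largest 5%/25% figures give 0.063 x 0.210 = 0.013 for claiming both. The marginal B figure matters where Cohort A truly works. The futility looks and the other caps were not simulated.

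**The case against.** Several counter-arguments carry weight.

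- **The option is discretionary.** A reader might infer that the primary ORR is enriched by design, or that the 0.025 test is invalid. The documents do not support that: the sponsor may cap, and Step 2 shows the level is kept when no type exceeds 15%. What remains is a gap between the enrolled mix and the stated population.
- **There is no reference mix.** The documents give no target tumor distribution, and the other caps and referral already shape enrollment. So the comparison can only be with the mix that would have enrolled without the response-driven cap. That comparison is still meaningful, because only this cap depends on the outcome.
- **Lag and the number of types shrink the effect.** Scans are every 9 weeks (Protocol 8.2.1), SAP 7.2.1 requires confirmed response, and Protocol Table 5 lists 19 tumor types of unequal frequency. This stands: in Cohort A the effect can vanish. In Cohort B it shrinks, and with twelve types can be negligible.
- **The largest figures could be read as the likely error rate.** They come from types at exactly 0% and 30% with immediate closure. Nothing in the documents supports those rates.
- **Tumor-type ORR may be planned elsewhere.** The SAP's display list is a guideline and parts of SAP 7.4 are redacted. Tumor type is summarized and best response is listed by participant, so the mix will be visible. It therefore cannot be said that no such analysis exists, only that SAP 7.2.2 does not require one.

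Against this, a cap for lack of benefit makes sense only if types are thought to differ, which is the condition under which the pooled ORR shifts.

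**Conclusion.** The point holds conditionally. If a tumor type is capped because no benefit is seen, and response rates differ by type with some above 15%, the pooled ORR is partly selected on its own outcome and can exceed 15% when the uncapped mix does not. The direction follows from the design; the size cannot be fixed from the documents, which give neither type-specific ORRs nor a closure rule. Under the 5%/25% assumptions the chance of success is about 1.5-6% (A) and 4-21% (B) with six types, and about 1-2% and 2.5-8% with twelve, against 1.4% and 2.4% without capping. Cohort B is more exposed, but is reached only through Cohort A. The issue is to whom the result applies, not a fault in the binomial test for the participants enrolled.

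**What to change.** Keep the sponsor's option, and make three changes.

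1. **SAP 7.2.2:** replace the optional wording with a required table of ORR by tumor type, with exact confidence intervals, for Cohorts A and B. Mark each type capped for lack of response and give the numbers enrolled before and after each cap.
2. **Protocol 4.1:** base any such cap on centrally reviewed response, and record its date and the data behind it.
3. **SAP, primary analysis:** state that, if a response-driven cap was used, the primary ORR and its p-value apply to the enrolled mix and not to all FGFR-altered solid tumors. Show, as a descriptive sensitivity, the ORR of participants dosed before the first such cap. In simulation with an uncapped ORR of 15% this is near 15% and slightly conservative.

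Two other remedies look attractive but should not be relied on. A written count rule alone leaves the inflation in place, because the figures above arise under exactly such a rule. An ORR reweighted to the pre-cap mix is biased downward, because types stopped at zero responders keep estimates near zero: with every type truly at 15%, closure after 0/5 and no lag, it averaged 10.4% in A and 9.5% in B. A rule requiring its lower confidence bound to exceed 15% would restrict valid conclusions.

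The cost is one more table, a small and imprecise sensitivity estimate, and a narrower claim if caps are used. Sample size and the primary test are unchanged. If no such cap is used, the record shows it and the concern closes.

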## 4.2. Overall Study Duration

The study begins when the first participant signs the ICF. The end of the study is defined as the date of the last visit of the last participant in the study.

Once the study has reached the target enrollment of at least 170 treated participants, if there are approximately  $\leq 3$  participants on study for more than 6 months, a database lock of the study may occur to allow the analysis of the study data. Any remaining participants may continue to receive study treatment and be seen by the investigator per Protocol. The investigator will be expected to monitor for and report any SAEs, AEs of special interest, and pregnancies, as detailed in Section 9. The remaining participants are considered to be on study until a discontinuation criterion is met and written notification is provided to the sponsor.

